7 STATISTICAL METHODOLOGY

7.1 Analysis Sets

Part I

The Safety Analysis Set will consist of all subjects who receive study treatment (vitrectomy/AAV8-RPGR). The Safety Analysis Set will be used for all analyses in Part I.

Part II

The Safety Analysis Set will consist of all subjects who are randomized, under both the 2and the 3-arm randomization schedules and receive study treatment when randomized to active treatment, or attend Visit 2 (telephone call) when randomized to control (no treatment). The Safety Analysis Set will be used for safety analyses in Part II. Subjects will be analyzed based on the actual treatment they received.

The Intent-to-Treat (ITT) Analysis Set will consist of all subjects who are randomized, under the 3-arm randomization schedules. The ITT Analysis Set will be used for efficacy analyses in Part II. Subjects will be analyzed based on the treatment to which they were randomized.

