- 4. Have participated in another research study involving an investigational product in the past 12 weeks or received a gene/cell-based therapy at any time previously (including but not limited to: Intelligent Retinal Implant System implantation, ciliary neurotrophic factor therapy, nerve growth factor therapy).

Test product, dosage, and mode of administration: Part I, Dose Escalation, Phase 1: All subjects will undergo vitrectomy and receive a single sub-retinal injection of AAV8-RPGR. Subjects will be assigned to 1 of the following AAV8-RPGR dose levels: 5×10^{9} vg, 1×10^{10} vg, 5×10^{10} vg, 1×10^{11} vg, 2.5×10^{11} vg, or 5×10^{11} vg.

Part II, Dose Expansion, Phase 2/3: Subjects will be assigned to 1 of the following: high-dose $(2.5 \times 10^{11} \text{ yg})$, low-dose $(5 \times 10^{10} \text{ yg})$, or an untreated control arm.

Reference therapy (Comparator), dosage, and mode of administration: In Part I, no reference therapies will be administered. In Part II, 2 doses of AAV8-RPGR will be compared: a high-dose $(2.5 \times 10^{11} \text{ yg})$ and a low-dose $(5 \times 10^{10} \text{ yg})$ to an untreated control arm.

Criteria for Evaluation:

Safety: The safety evaluation will be based on adverse event reporting (including DLTs); full ophthalmic examination (including indirect ophthalmoscopy, slit-lamp examination, intraocular pressure [IOP], anterior chamber and vitreous inflammation grading and lens opacities classification system III [LOCS III] cataract grading); fundus photography; vital signs; and laboratory assessments (including laboratory safety parameters, viral shedding and immunogenicity).

Any safety information collected as a result of the efficacy assessments (e.g., BCVA) will also be used in the overall safety evaluation, as appropriate.

Efficacy: The efficacy evaluation will be based on microperimetry (MAIA), BCVA, SD-OCT, fundus autofluorescence, visual fields (Octopus 900 specified in Part II only), contrast sensitivity, low luminance visual acuity (LLVA),

Statistical Methodology:

In Part I, the safety analysis set will include all patients enrolled in the study who received AAV8-RPGR treatment.

All analyses in Part I will be performed using the Safety Analysis Set.

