8.4. Vitrectomy Procedure and Injection of AAV8-RPGR

The subretinal injection technique to be used in this study is similar to that developed in the sponsor's choroideremia programme in Oxford and other international investigator-sponsored trials in the United States, Canada and Germany. To date, over 200 subjects have been injected without complication by retinal surgeons using the technique described below.

All subjects may be treated at the time of surgery with up to 1 mL of triamcinolone (40 mg/mL), administered via a deep sub-Tenon approach.

[figure not shown]
Injection of AAV8-RPGR is to be performed by an appropriately qualified and experienced retinal surgeon. All surgeons must have completed all study-specific surgical training and obtained certification by NightstaRx to perform the study procedure, before treating a study participant.

Initially, subjects will undergo a standard vitrectomy and detachment of the posterior hyaloid (Figure 2). All surgery will be conducted using the standard BIOM vitrectomy system. A 23-gauge sutured approach is usually favored to avoid any potential risks of wound leakage. Prior to sub-retinal injection of AAV8-RPGR, the retina will be detached with 0.1-0.5 mL of balanced salt solution (BSS) injected through a 41-gauge sub-retinal cannula connected to a vitreous injection set. A single dose of AAV8-RPGR will be injected into the sub-retinal fluid through the same entry site. If detachment of the macula occurs with a smaller volume of fluid, then additional subretinal sites in the posterior globe (e.g., nasal to the disc) may also be chosen to deliver up to the entire 0.1 ml of vector. This avoids excessive foveal stretch.

If unexpected complications of retinal detachment are encountered (e.g., macular hole created requiring treatment with gas), the injection of vector can be deferred until a later date.

Subjects will be carefully monitored for the occurrence of AEs peri- and post-operatively. All AEs, irrespective of relationship to the study drug and/or the surgical procedure will be captured in the subject's medical record and reported in the eCRF.

Figure 2 Sub-retinal Injection of AAV8 Vector

(A) A standard vitrectomy through the BIOM operating system to remove the vitreous gel is followed by (B) retinal detachment by injection of BSS and injection of up to 0.1 mL vector suspension through a 41-gauge cannula into the sub-retinal space.

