9.2. Visit 2 (Day 0, Surgery/Injection Day Visit)

At Visit 2, all subjects in the AAV8-RPGR groups will visit the surgical site, and the following assessments will be performed prior to surgery:

• Full ophthalmic examination, including indirect ophthalmoscopy, slit lamp examination with IOP assessment, anterior chamber, and vitreous inflammation grading, and LOCS III cataract grading

- Blood pressure and pulse
- AE/SAE monitoring
- Review of concomitant medication, treatments, and procedures
- Corticosteroid compliance review¹
 - 1. Corticosteroid review is applicable only for treated subjects.

It may be necessary for subjects to undergo a pre-surgical workup according to local hospital procedures (e.g., blood draw for anesthetist) which are outside of the protocol-defined assessments. Any assessments performed outside of the protocol will not be collected as part of the study analyses.

Subjects will then undergo vitrectomy and receive a sub-retinal injection of AAV8-RPGR (see Section 8.4 for details).

Subjects may be treated at the time of surgery with up to 1 mL of triamcinolone (40 mg/mL), administered via a deep sub-Tenon approach.

Subjects will be carefully monitored for the occurrence of AEs during the procedure. Subjects may stay overnight or return to the site 1 day and then 7 days after surgery for post-operative follow-up (Visits 3 [Day 1] and 4 [Day 7], respectively).

Subjects in the Control group will receive a study visit Telephone Call at the agreed upon date and time. Sites will conduct the following assessments during the telephone call:

- AE/SAE monitoring
- Review of concomitant medication, treatments, and procedures

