7.11 Exposure

As the treatment consists of a single injection, exposure to study medication will not be applicable.

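### The Part II Safety Set leaves out a randomised control who misses the Day 0 telephone call, even if he is then followed to Month 12

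*SAP*

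**What the plan says.** The Part II Safety Analysis Set has one entry condition for each kind of arm. A subject randomised to a dose must "receive study treatment when randomized to active treatment". A control must be randomised "or attend Visit 2 (telephone call) when randomized to control (no treatment"). SAP 7.1, Protocol 12.3.1 and the statistical methodology part of the synopsis agree on this. The further rule, that subjects are analysed by the treatment they actually received, only assigns subjects already in the set to a column.

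For controls, Visit 2 is a call and nothing else: "Subjects in the Control group will receive a study visit Telephone Call at the agreed upon date and time" (Protocol 9.2). During it the site asks about adverse events and reviews concomitant medication and procedures. Controls first come to the clinic after randomisation at Month 1 (Protocol 8.6 and 9.5) and are followed for 12 months.

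The ITT set in SAP 7.1 is everyone randomised under the three-arm scheme, with no call or treatment condition.

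On the dosed side, the Part I definition in SAP 7.1 explains the term in passing: "The Safety Analysis Set will consist of all subjects who receive study treatment (vitrectomy/AAV8-RPGR"). The Part II sentence uses the same term without an explanation. Protocol 8.4 foresees that after a complication of the retinal detachment "the injection of vector can be deferred until a later date".

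**The concern.** Missing one telephone contact loses what that contact would have recorded. It is not a reason to discard the following year of data. Protocol 11.2.2 collects adverse events from consent, so a control who missed the call and attended from Month 1 would have nearly complete safety data. Under the written rule none of it reaches a Safety Set table.

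The set is also used for demographics and baseline ocular characteristics (SAP 7.8, Protocol 12.5), and for ocular history and medications (SAP 7.9 and 7.10). The baseline table and the efficacy tables would then describe different control groups. The untreated arm exists to allow a controlled comparison of safety as well as efficacy, and it is small, so one subject matters to its descriptive rates.

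A lesser question concerns a dosed-arm subject who had surgery but no vector. Part II does not say outright whether he has received study treatment, or which column he belongs to.

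**Working it through.** **1. The plan's own figure.** The only design figure nearby is the power in SAP 6.6: about 87% with 10 treated and 9 control subjects, response rates 50% and 5%, one-sided 0.10, Boschloo test with a Berger-Boos constant of 0.001. Power is the sum over all outcomes (x₁, x₂) of Bin(x₁; 10, 0.50) × Bin(x₂; 9, 0.05) where the test rejects. Exact enumeration gives 86.8%, so the figure reproduces. It does not depend on the Safety Set, because the primary analysis uses ITT.

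**2. Following one control through the rules.** Take a control who is randomised, misses the Day 0 call, and attends Month 1 to Month 12.

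- ITT (SAP 7.1): in, because randomisation under the three-arm scheme is the only condition.
- Safety Set (SAP 7.1, Protocol 12.3.1, synopsis): out, because the call is the only way in for a control.
- Adverse event and examination tables (SAP 7.13): out, because all use the Safety Set.
- Demographic and baseline tables (SAP 7.8): out.
- Efficacy tables (SAP 7.12.1): in.

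**3. Size, assuming one excluded control.** The input is 9 controls, from SAP 6.6.

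- Share of the comparator lost: 1/9 = 11.1%, leaving 8.
- Upper 95% Clopper-Pearson limit for an event never seen, 1 − 0.025^(1/n): 33.6% for n = 9 and 36.9% for n = 8.
- Chance of seeing at least one case of an event with a true incidence of 10% (an assumed rate), 1 − 0.9^n: 61.3% for n = 9 and 57.0% for n = 8.
- If he had the arm's only case of some event, the untreated column changes from 1/9 (11.1%) to 0/8.

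**4. The dosed-arm wording, side by side.**

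- Part I definition, SAP 7.1 and Protocol 12.3.1: vitrectomy/AAV8-RPGR. The slash can be read as and, or as or.
- Protocol 12.7: explains study treatment as surgery/study drug.
- SAP 7.13.1: counts treatment-emergent events from the day of surgery.
- SAP 7.11: "As the treatment consists of a single injection", which points to the injection alone.
- Synopsis, on Part I only: "all patients enrolled in the study who received AAV8-RPGR treatment", which also points to the vector.

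The first three favour keeping a subject who was operated on. The last two favour the injection reading, but one concerns exposure and the other Part I.

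For scale, the Safety Set also takes in the three subjects randomised 2:1 under Version 6 (SAP 6.1). If they split two high and one low and all were treated (an assumption), the dosed arms would hold about 10 + 2 = 12 and 10 + 1 = 11. One such subject's event would then be 1/12 = 8.3% or 1/11 = 9.1%, against zero if he were left out.

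**The case against.** The best defence is that the call is the control's Day 0 event, just as surgery is for a treated subject. It monitors adverse events, and SAP 7.10 uses Visit 2 (Day 0) in place of the surgery date for controls. A common Day 0 entry point is reasonable, and it would be wrong to say that the call has no bearing on safety. This explains why a Day 0 anchor is used. It does not explain why a missed contact should remove everything that follows.

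The case may also be rare or absent. Protocol 9.2 gives no window for the call, so a late one might still count as Visit 2. Enrolment closed on 30 September 2019 and Visit 2 was due within 12 weeks of screening. The calls were therefore due well before Protocol Version 11 (1 October 2020) and the March 2021 SAP. Nothing in the documents suggests that a control missed his call. This stands, and it limits the point to a rule that could exclude someone.

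A reader might infer that such a control disappears from the report altogether. He does not. His microperimetry, BCVA change and SD-OCT findings stay in the efficacy tables, which use ITT. SAP 5.2.2.3 also lists letter losses as secondary endpoints, although the table of losses is specified under safety.

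A reader might also infer that a dosed-arm subject who was operated on but not injected is excluded. The documents do not support that as a definite exclusion. The Part I explanation stands just before the Part II sentence, Protocol 12.7 and the treatment-emergent definition point the same way, and Protocol 8.4 speaks of deferring the vector, not of never giving it. A macular hole in such an eye would still appear in the SD-OCT summaries of SAP 7.12.5 under ITT, provided he attended. What remains is an ambiguity worth one clarifying phrase.

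**Conclusion.** The point holds for controls, on the literal text of all three places. A control who misses the Day 0 call is outside the Safety Set however long he is followed. His adverse events and his demographic and baseline data drop out of the tables while his efficacy data stay in.

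One exclusion would cost 11% of a 9-subject comparator. That rests on the planned control number and on an assumed count of one. Safety is descriptive, with no formal testing, and neither the primary test nor its power changes.

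For dosed-arm subjects who were operated on but not injected, the documents are unclear but lean towards inclusion, so only a clarification is needed.

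**What to change.** Use the same sentence in SAP 7.1, Protocol 12.3.1 and the synopsis. For controls, include every randomised control with any study contact or assessment on or after Day 0, defined as the scheduled Visit 2 date, whether or not the Visit 2 call was completed. The Day 0 limit matters. Randomisation takes place at Visit 1, up to 12 weeks earlier, and a rule based on any contact after randomisation would admit controls who withdrew before Day 0. The same date can serve as the control's reference for treatment-emergent events, which SAP 7.13.1 defines only by the day of surgery.

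As a secondary clarification, state that in Part II study treatment means that study surgery was started, whether or not vector was injected. Tabulate any operated-but-not-injected subject, with a flag, among treated subjects and not as untreated.

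The cost is one aligned sentence in three places, with no new data and no change in conduct. The small downside is that a flagged subject who received no vector may be counted among treated subjects. If neither case occurred, no result changes.

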7.2 Conventions

Summary statistics will be presented for both eyes (study eye versus fellow eye). In Part I, no formal statistical comparison will be performed. In Part II, formal statistical testing will be performed.

Continuous variables and their change from baseline will be summarized using descriptive statistics (number of subjects[n], mean, standard deviation, median, minimum and maximum, first and third quartiles, fifth and ninety-fifth percentiles). The confidence intervals (CIs) of the mean and the mean change from baseline at each visit may be provided where applicable. If CI is reported, the CI of the mean value is calculated by one sample t-test, and the CI of mean change from baseline is calculated by paired t-test. For categorical variables, the number and proportion of subjects pertaining to each category will be presented. The CIs of the proportion may be provided where applicable. In the event of CI of the proportion is reported, it is calculated by the Clopper-Pearson method.

Age is calculated as (Informed consent date – date of birth + 1)/365.25 and displayed as an integer. If the day and month of birth are not known, the date of birth will be imputed as 01July of the birth year.

7.3 Time Points and Visit Windows

The study baseline is defined as the most recent non-missing measurement (scheduled or unscheduled) prior to the study treatment. Where this value is missing or unavailable, then an available Visit 2 (prior to treatment) result will be used.

Change from baseline is defined as the difference between an assessment at the considered visit and the baseline.

Study Day 0: the date of the surgery

Study Day is calculated as:

- For a date on or after Study Day 0
- Study Day = (Date of Interest) (Study Day 0) + 1
- For a date before Study Day 0
- Study Day = (Date of Interest) (Study Day 0)

All data will be analysed using nominal study visits as defined in the Study Schedule and eCRF. However if the study visits from Month 24 for Part I and Month 12 for Part II are collected within 6 months out of window, these visits will be included in the analysis.

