6.1.1. Dose-Limiting Toxicity

DLTs are defined as any of the following events considered to be related to AAV8-RPGR and should be reported to the sponsor:

- Sustained decrease in BCVA of ≥30 letters on the Early Treatment of Diabetic Retinopathy Study (ETDRS) chart compared to baseline; sustained is defined as lasting 48 hours or more until recovery, with recovery defined as visual acuity (VA) returning to within 10 letters of baseline VA. An exception is made for surgery-related events occurring in close temporal association (within <24 hours) of the surgery.

- Vitreous inflammation, vitritis (>Grade 3 using standardised Nussenblatt vitreous inflammation scale grading) (Nussenblatt, Palestine et al. 1985)

AAV8-RPGR Version 11.0 Protocol: NSR-RPGR-01 1 Oct 2020

 Any clinically significant retinal damage observed (e.g., retinal atrophy) that is not directly attributed to complications of surgery

• Any clinically relevant suspected unexpected serious adverse reaction (as defined in the Investigator's Brochure), with the exception of vision loss or vision-threatening events (as defined in Section 11.2.1.2)

[figure not shown]
When triplicate BCVA assessments are performed at screening, the median BCVA result will be used for change-from-baseline BCVA computation.

If a DLT occurs at any time during the study, the site is to report the event to the sponsor within 24 hours of occurrence. A DLT will be reported by the investigational site, to the sponsor via a DLT/serious adverse event (SAE) reporting form that must be completed as fully as possible and emailed to within 24 hours of being made aware of the event. Only 1 DLT/SAE form must be completed for each DLT.

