9.14. Unscheduled Visits

If clinically indicated, subjects may need to return to the site for an unscheduled visit. At a minimum, the following assessments will be performed.

- Full ophthalmic examination, including indirect ophthalmoscopy, a slit-lamp examination, IOP, anterior chamber and vitreous inflammation grading and LOCS III cataract grading
- ETDRS BCVA¹
- SD-OCT
- Fundus autofluorescence
- MAIA microperimetry, if clinically feasible¹
- AE/SAE monitoring
- Review of concomitant medication, treatments, and procedures
 - 1. For unscheduled visits that occur during Part II, BCVA and microperimetry will be conducted by qualified masked assessors from Month 3 through Month 12.

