12.7.2. Ocular Safety Evaluations

IOP and changes from baseline in IOP, abnormal slit lamp examination findings and indirect ophthalmoscopy findings, and anterior chamber and vitreous inflammation grading will be summarised by visit and eye.

Lens opacity categories and shifts from baseline will be summarised by visit and eye.

Categories of fundus photography findings (none/mild/moderate/severe) will be summarised by visit and eye.

The number of subjects with a 5, 10 and 15letter decrease from baseline in BCVA will be tabulated by visit and by eye.

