7.13.2 Best-Corrected Visual Acuity (BCVA)

Part I and Part II

The proportion of eyes with a \geq 5 letters, a \geq 10 letters and a \geq 15 letters decrease from baseline will be summarized by treatment groups, visits, and eyes.

When there are more than one BCVA measurement at the same visit, the median value will be used for the purpose of the analysis.

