7.13.5 Slit Lamp Examination

Part I and Part II

The number and percentage of subjects within each category of slit lamp examinations outcomes will be summarized by treatment groups, visits and eyes.

The shift for 'Cornea', 'Conjunctiva', 'Iris', 'Lens' and 'Anterior Segment' will be summarized from "Normal/Clinically insignificant abnormality" or "Clinically significant abnormality" at baseline to "Normal/Clinically insignificant abnormality", or "Clinically significant abnormality" at any post-baseline visit.

The categories for the shift from baseline for 'Anterior chamber, hypopyon', 'Grading of anterior chamber cells', 'Grading of anterior chamber flare' and 'Vitreous inflammation quantification' assessments are defined as follow:

- Absent at Baseline to absent
- Absent at Baseline to present
- Present at Baseline to absent
- Present at Baseline to present

For 'Grading of anterior chamber cells' assessment, absent is defined as '0 Cells' and present is defined as any other category (except missing).

For 'Grading of anterior chamber flare' assessment, absent is defined as 'Complete absence' and present is defined as any other category (except missing).

For 'Vitreous inflammation quantification' assessment, absent is defined as '0' and present is defined as any other category (except missing).

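### An eye's worst post-baseline BCVA loss, IOP or inflammation grade has no specified summary table: BCVA loss and IOP are tabulated by visit, and inflammation shifts are absent/present.

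*SAP*

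**What the plan says.** SAP 7.3 sets the time-point rule: "All data will be analysed using nominal study visits as defined in the Study Schedule and eCRF". The one stated exception admits a Month 12 (Part II) or Month 24 (Part I) visit made up to 6 months out of window. The same section defines baseline as the "most recent non-missing measurement (scheduled or unscheduled) prior to the study treatment", so unscheduled values are named for baseline, but nothing is said about them after baseline.

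Protocol 9.14 provides for extra visits: "If clinically indicated, subjects may need to return to the site for an unscheduled visit". Their minimum content includes BCVA, SD-OCT and a full ophthalmic examination with IOP and inflammation grading.

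The safety tables are these:
- **BCVA loss (SAP 7.13.2).** The proportions with a 5, 10 or 15 "letters decrease from baseline will be summarized by treatment groups, visits, and eyes".
- **IOP (SAP 7.13.6).** Values and change from baseline, by group, visit and eye.
- **Slit lamp (SAP 7.13.5).** "The number and percentage of subjects within each category of slit lamp examinations outcomes will be summarized by treatment groups, visits and eyes". Protocol 12.7.2 likewise says that "anterior chamber and vitreous inflammation grading will be summarised by visit and eye".
- **Inflammation shifts (SAP 7.13.5).** Absent or present only, for cells, flare and vitreous inflammation. "For 'Vitreous inflammation quantification' assessment, absent is defined as '0' and present is defined as any other category (except missing".

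**The concern.** A safety reader wants to know how far each eye fell, or how inflamed it became, at its worst. The specified measurement tables do not answer that. A by-visit table gives the distribution at each visit and does not follow one eye to its worst value. A binary shift puts a minimal vitreous grade and one above Grade 3 (the DLT level in Protocol 6.1.1) in the same cell, and it shows no change at all for an eye that starts at a low non-zero grade and worsens.

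Unscheduled visits happen because something is clinically wrong, yet their measurements have no assigned output. The SAP does use the missing principle elsewhere: under 7.13.10.1, one markedly abnormal laboratory value at any post-baseline time counts the subject.

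The arms are small. The sample-size section (SAP 6.6) works with 10 subjects in a dose group and 9 controls, so one eye moves a proportion by 1/10 = 10 or 1/9 = 11 percentage points.

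**Working it through.** The plan states no figure on this point, so there is none to reproduce. The check sets the rules side by side and then sizes the gap by illustration.

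**1. Is there a home for the worst measured value?**
- BCVA loss (7.13.2) and IOP (7.13.6): by visit; no worst post-baseline row.
- Cells, flare and vitreous inflammation (7.13.5): category counts by visit, plus a binary shift; no worst-grade table.
- Laboratory data (7.13.10.1): explicit any-post-baseline rule.
- Ophthalmoscopy (7.13.4): shifts to any post-baseline visit.
- Adverse events (7.13.1): not tied to visits, but Protocol 11.2.2 grades severity as mild, moderate or severe by effect on activities, not by letters lost or inflammation grade.

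For BCVA loss, IOP and inflammation grade, the answer is no.

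**2. How often would a by-visit table see a short episode?**

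Inputs: nominal on-site visits for a treated subject at Days 1 and 7 and Months 1, 2, 3, 6, 9 and 12. With a month of 365.25/12 = 30.4 days, these fall on Days 1, 7, 30, 61, 91, 183, 274 and 365. Assumptions: episode length D, onset uniform over the period, visits on their nominal day.

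Within a gap of length G between visits, an episode is still present at the next visit if its onset lies in the last min(D, G) days. The probability over a period is the sum of min(D, G) over its gaps, divided by the length of the period.

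After Month 3 every gap is about 91 days:
- D = 14: 14/91 = 15%.
- D = 28: 28/91 = 31%.

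From Day 1 to Month 3 (about 90 days) the gaps are 6, 23.4, 30.4 and 30.4 days:
- D = 14: (6 + 14 + 14 + 14)/90 = 48/90 = 53%.
- D = 28: (6 + 23.4 + 28 + 28)/90 = 85.4/90 = 95%.

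Controls are telephoned on Days 0, 1 and 7 (Protocol 9.2 to 9.4), so their only on-site visits in that period are Months 1, 2 and 3. For D = 14 this gives (14 + 14 + 14)/90 = 42/90 = 47%.

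The early post-operative period is therefore reasonably covered by the schedule. The thin coverage is after Month 3.

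**The case against.** The strongest reply is that the safety evaluation does not rest on these tables. The Part II safety endpoint is TEAE incidence. Subjects are asked about adverse events at every visit, including unscheduled ones (Protocol 11.2.2). SAP 7.13.1 tabulates inflammation-related and reduced-visual-acuity TEAEs with time to onset, SAEs, DLTs and maximum severity, none of them by visit. Sustained non-surgery-related loss of 15 letters or more must be reported as an SAE (Protocol 11.2.1.2). Sustained loss of 30 letters or more, or vitritis above Grade 3, is a DLT if related to the vector, subject to the early surgical exception for vision loss.

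All of this stands, and it rules out several stronger readings a reader might infer:
- **That safety results are tabulated at nominal visits only, or that a worst event reaches no summary table.** The adverse-event tables and the any-post-baseline shifts contradict this. What they do not give is size: an SAE of at least 15 letters is not a number of letters, and smaller losses have no mandatory reporting threshold of this kind.
- **That inflammation grades are not tabulated.** They are counted by visit. The loss is in the binary shift and in the link from baseline to an eye's worst grade.
- **That unscheduled values are expressly excluded.** They are not. Table 3 of the protocol lists the unscheduled visit as a column, so exclusion is an inference from silence. If that column were treated as one visit, though, the median rule in 7.13.2 could average several unscheduled BCVA values and dilute the worst.
- **That unscheduled LLVA is lost.** LLVA is not among the minimum assessments at those visits.
- **That the worst events will mostly be seen at unscheduled visits.** The documents give no data on this.

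The reply also limits the remedy. Only treated subjects have BCVA scheduled on Days 1 and 7, and Protocol 6.3 expects transient visual impairment after vitrectomy. A worst-value row with no time cut would mix that loss into a comparison with controls who were telephoned.

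**Conclusion.** The gap is real but narrow. As the SAP stands, the measured size of the worst post-baseline BCVA loss, IOP or inflammation grade, including values from unscheduled visits, has no specified summary. That an event occurred is captured if it is reported as an adverse event, and by-visit grade counts exist.

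The loss falls mainly on short episodes after Month 3. An assumed 14-day episode is present at a scheduled visit with probability about 15% then, against about 53% (treated subjects) for onset between Day 1 and Month 3. These figures are illustrations: they rest on assumed durations, uniform onset and visits on the nominal day. It would be wrong to carry the late-period miss rate over to the whole follow-up; over the full year a 14-day episode is seen about 25% of the time and a 28-day episode about 47%. A lasting loss would appear at the next scheduled visit.

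Safety analyses are descriptive, without formal testing (Protocol 12.7), and the primary efficacy analysis is unaffected. This is a cheap improvement to safety reporting.

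**What to change.** - **SAP 7.3.** State that post-baseline unscheduled and early termination values enter the worst-value summaries.
- **SAP 7.13.2 and 7.13.6.** Add a worst post-baseline row for BCVA loss (at least 5, 10 and 15 letters) and for IOP, counted from Month 1 onward, the first on-site post-baseline visit in all arms. Show the earlier post-operative period, whose Day 1 and Day 7 visits are on site for treated subjects only, separately.
- **SAP 7.13.5.** Replace the absent/present shift for cells, flare and vitreous inflammation with baseline grade by worst post-baseline grade, using the same split.
- **Keep the by-visit tables** and report the number of unscheduled visits per arm. Dosed eyes may be examined more often than control eyes, and more examinations give more chances to record a bad value.

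The cost is SAP wording and a few descriptive outputs from data the protocol already collects.
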